#### **8.2 Procedures for recording and reporting adverse events (AE)**

*8.2.1 Definitions in Law of May 7, 2004 concerning experiments on the human person*

**Adverse reaction (AR):** all untoward and unintended responses to an investigational medicinal product or to an experiment and, when an investigational product is concerned, related to any dose administered;

**Adverse event (AE):** any untoward medical occurrence in a patient or subject of the treated group during an experiment, and which does not necessarily have a causal relationship with this treatment;

**Unexpected adverse reaction (UAR):** an adverse reaction, the nature or severity of which is not consistent with the information on the experiment, and, when a clinical trial is concerned, with the applicable product information (e.g. investigator's brochure for an unauthorized investigational

product or the patient leaflet joined to the summary of product characteristics for an authorized product);

**Serious adverse event (SAE) or serious adverse reaction (SAR):** any untoward medical occurrence or effect that results in death, is life-threatening, requires hospitalisation or prolongation of existing hospitalisation, results in persistent or significant disability or incapacity, or is a congenital anomaly or birth defect, and this, when it is a clinical trial, at any dose;

**Suspected unexpected serious adverse reaction (SUSAR):** is an AR that is serious and unexpected (meaning that nature or severity of the AR is not consistent with the Investigational Medicinal Product reference safety information, which is the Investigator's Brochure) and is judged by either the investigator or the sponsor as having a reasonable suspected causal relationship with the investigational medicinal product.

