### **3.6 Trial Design**

It will be a prospective non-randomised control study in which patients are evenly divided into the telecoaching group or usual care group according to owning a smartphone and their affinity with it. It is not possible to fully blind the investigator and patients. The trial will consist of 4 visits. An outpatient clinic visit (V1), a screenings visit (V2), a third visit (V3) at which the intervention will start and where the patients will be divided into the control or the intervention group and a final visit (V4) 8 weeks after starting up the intervention (V4).

Patients in both groups will receive a brochure during V3 explaining the importance of physical activity with recommendations to improve it. This brochure will be discussed together with the patients.

In the intervention group patients will receive the usual care in combination with the telecoaching intervention consisting of the following components: 1: motivational interview with the investigator during V3 discussing motivation, barriers, favourite activities and strategies to become more active; 2: a pedometer giving direct feedback on the amount of steps; 3: the coaching application linked to the step counter, which will be installed on the patient's smartphone. 4: telephone contact when a patient is non-compliant with either the use of the coaching intervention or with achieving the PA goals for 2 consecutive weeks.

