## 4. Trial intervention

### 4.1 Investigational Medicinal product and dosing regimen

#### Telecoaching intervention:

The intervention group receives a step counter together with a coaching application installed on their smartphone. This application is a renewed version of the program used in a previous coaching trial, conducted by our research group (Demeyer 2017) and is based on the basic principles of behavioral change and contains four major domains.

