### 4.2 Drug accountability

Not applicable.

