#### *8.2.3 Notification of serious adverse reactions*

The sponsor shall ensure that all relevant information about suspected unexpected serious adverse reactions that are fatal or life-threatening is recorded and reported as soon as possible to the minister, to the competent authorities in all the Member States concerned in the case of a trial, and to the competent ethics committee, and in any case no later than seven days after knowledge by the sponsor of such a case, and that relevant follow-up information is subsequently communicated within an additional eight days.

All other suspected unexpected serious adverse reactions shall be reported to the minister, to the competent authorities of all Member States concerned in the case of a clinical trial and to the ethics committee concerned as soon as possible but within a maximum of fifteen days of first knowledge by the sponsor.

The sponsor shall also inform the other investigators.

Once a year throughout the experiment, the sponsor shall provide the minister and the ethics committee in Belgium and those of the member States in whose territory the trial is conducted in the case of a multicentre trial, with a listing of all suspected serious adverse reactions which have occurred over this period and a report of the subjects' safety.

Regarding those adverse events and serious adverse reactions the Principal Investigator will take all reasonable measures, in consultation with Sponsor, to protect subjects at risk following the occurrence of such events.

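### The SUSAR definition in section 8.2.1 depends on a medicinal product and an Investigator's Brochure that this study does not have, so read literally the 7-day and 15-day reports cannot be triggered

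*Protocol*

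**What the plan says.** Section 8.2.1 of the protocol defines a SUSAR as a serious adverse reaction that meets two further conditions. Its nature or severity must be "not consistent with the Investigational Medicinal Product reference safety information, which is the Investigator's Brochure". The investigator or the sponsor must also judge it as "having a reasonable suspected causal relationship with the investigational medicinal product".

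The same section gives wider definitions just above. An adverse reaction (AR) may be a response to a medicinal product or to an experiment. An unexpected adverse reaction (UAR) is judged against the information on the experiment, with product information added only where a clinical trial is concerned.

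Section 8.2.3 attaches the expedited duties to this class of event. The sponsor must ensure that all relevant information about "suspected unexpected serious adverse reactions that are fatal or life-threatening is recorded and reported as soon as possible", within seven days at most. All other SUSARs have a limit of fifteen days.

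The intervention is described in sections 3.6 and 4.1. "The intervention group receives a step counter together with a coaching application installed on their smartphone". To this are added a "motivational interview with the investigator during V3 discussing motivation, barriers, favourite activities and strategies to become more active" and telephone contact in case of non-compliance. This text stands under the heading "Investigational Medicinal product and dosing regimen", but the next subsection, "Drug accountability", is marked as not applicable.

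**The concern.** A reporting rule should be able to catch the events that the study could plausibly cause. Patients with stage III or IV lung cancer are coached to walk more, with goals that can rise by 500 or 1000 steps per day each week (section 4.1). Both groups also perform study walk tests. A serious and unexpected event attributed to either activity is what an expedited route exists for. Here the definition behind that route points to a product and a reference document that are absent.

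Two things are at stake. The ethics committee and the minister could learn of such an event much later than the timetable in section 8.2.3 suggests. The investigator and sponsor are also asked for a causality judgement against something that does not exist, while the activities that could cause harm are not named.

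**Working it through.** No arithmetic lies behind the definition, and there is no stated figure to reproduce. The check sets the definitions beside the intervention and the reporting duties.

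1. **Conditions for a SUSAR (section 8.2.1).** An event must be (a) an AR, (b) serious, (c) inconsistent with the brochure for the product, and (d) suspected to be caused by the product.

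2. **Is there a product or a brochure?** The components in sections 3.6 and 4.1 are an interview, a step counter, an application and telephone calls. None is a medicinal product, drug accountability does not apply, and the protocol identifies no brochure for the programme. So (d) cannot be met, and (c) has nothing to be measured against.

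3. **Are the neighbouring definitions limited in the same way?** No.
   - AR: reaches responses to an experiment. Dose matters only when a product is concerned.
   - UAR: the reference is the information on the experiment. Product information is conditional.
   - Serious adverse event or reaction: the dose wording is again conditional on a clinical trial.
   - SUSAR: product and brochure are required without condition, and the experiment is not mentioned.

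4. **A test case.** Take a life-threatening, unexpected event during a study 6-minute walk test that is judged related to the test. It is an AR (response to the experiment), a UAR (not foreseen in the information on the experiment) and a serious adverse reaction. It fails (d), so it is not a SUSAR. The same holds for an event attributed to the coaching.

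5. **Exposure.** There are 32 patients, 16 coached and 16 controls (section 9.1). Each does two walk tests at visit 3, and all visit 3 assessments are repeated at visit 4 (sections 3.4 and 6.1): 2 + 2 = 4 tests per patient, and 32 × 4 = 128 tests if all complete. The coached group also has 8 weeks of the programme.

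6. **What each reporting route does with the test case.**
   - Immediate report to the sponsor (section 8.2.2): applies, because it covers serious adverse events with no causality condition.
   - 7-day or 15-day report (section 8.2.3): does not apply, because it depends on the SUSAR class.
   - Yearly listing to the minister and ethics committee (section 8.2.3): applies, because it covers suspected serious adverse reactions, and AR includes reactions to an experiment.
   - On request: further information on deaths goes to the ethics committee, and adverse event records go to the minister (section 8.2.2).

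Only the expedited route is empty. The fallback that reaches the ethics committee without a request is annual, while one patient's participation lasts at most 8 + 2 = 10 weeks (section 5.4). A patient can therefore finish the study well before the listing that reports the event.

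**The case against.** The strongest reply is that the literal reading is too strict. Section 8.2.3 spells the term out instead of using the abbreviation, and the words that make it up are each defined in a way that reaches an experiment. Its references to a trial qualify only the duties towards other Member States, so the duties to the minister and ethics committee can be read as covering experiments generally. The heading of section 4.1 might let a site treat the programme as the product. Section 8.2.1 presents itself as definitions from the 2004 Law, and section 12 commits the study to all applicable requirements, so a careful sponsor might report anyway.

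Part of this stands. A sensible reader could reach the right result, and what the Law itself requires of a non-drug experiment cannot be settled from the protocol. But the protocol gives SUSAR its own explicit definition, and the reader must set it aside to get there. The section 4.1 heading does not rescue it: it supplies no brochure, and it would not cover walk tests done as assessments in both groups.

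A reader might also infer something stronger: that serious events stop at the sponsor, or that the pilot would report no suspected serious reactions at all and so give false reassurance to the larger trial. The protocol does not support this. The immediate report and the yearly listing do not use the SUSAR definition, so these events would be recorded and would reach the authority and the ethics committee.

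Nor is the mention of a brochure in section 8.2.2 a further defect. It is one of two possible sources of exemptions from immediate reporting, and a brochure that does not exist exempts nothing.

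**Conclusion.** The point holds for the expedited route only. Section 8.2.1 contradicts itself: a serious unexpected reaction to the experiment meets the AR, UAR and serious adverse reaction definitions, yet cannot meet the SUSAR definition. Taken literally, the number of events that could qualify for a 7-day or 15-day report is zero, whatever happens among the 32 patients. The loss is one of timeliness, not of reporting as such.

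This rests on two assumptions: that staff apply the SUSAR definition as written, and that no brochure for the telecoaching programme exists outside the protocol. A brochure would repair the expectedness condition but not the causality condition. The primary endpoint, the sample size and the analysis are not affected.

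**What to change.** Reconcile the SUSAR definition in section 8.2.1 with the AR and UAR definitions beside it:

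- Refer causality to the experiment, stated as the telecoaching intervention or study procedures such as the walk tests.
- Refer expectedness to the information on the experiment, in place of the Investigator's Brochure.
- Ask that the causality of each serious event be assessed on that basis.

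Sections 8.2.2 and 8.2.3 can stay as they are. The cost is a short wording amendment and, now and then, an expedited report that the present text would not produce.

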#### *8.2.2 Notification of adverse events*

The investigator shall report all serious adverse events immediately, after first knowledge, to the sponsor except for those that the protocol or investigator's brochure identifies as not requiring immediate reporting. The immediate report shall be followed by detailed, written reports. The immediate and follow-up reports shall identify subjects by code numbers.

For reported deaths of a subject, the investigator shall supply the sponsor and the accredited ethics committee with any additional information requested.

The sponsor shall keep detailed records of all adverse events which are reported to him by the investigator or investigators. These records shall be submitted to the minister if the experiment is being conducted in Belgium, if he so requests.

#### *8.2.3 Notification of serious adverse reactions*

The sponsor shall ensure that all relevant information about suspected unexpected serious adverse reactions that are fatal or life-threatening is recorded and reported as soon as possible to the minister, to the competent authorities in all the Member States concerned in the case of a trial, and to the competent ethics committee, and in any case no later than seven days after knowledge by the sponsor of such a case, and that relevant follow-up information is subsequently communicated within an additional eight days.

All other suspected unexpected serious adverse reactions shall be reported to the minister, to the competent authorities of all Member States concerned in the case of a clinical trial and to the ethics committee concerned as soon as possible but within a maximum of fifteen days of first knowledge by the sponsor.

The sponsor shall also inform the other investigators.

Once a year throughout the experiment, the sponsor shall provide the minister and the ethics committee in Belgium and those of the member States in whose territory the trial is conducted in the case of a multicentre trial, with a listing of all suspected serious adverse reactions which have occurred over this period and a report of the subjects' safety.

Regarding those adverse events and serious adverse reactions the Principal Investigator will take all reasonable measures, in consultation with Sponsor, to protect subjects at risk following the occurrence of such events.

### **8.3 Treatment stopping rules**

Not applicable.

## **9 Statistics**

### **9.1 Sample size**

We will include 16 patients motivated for a coaching program and compare them with a matched control group of 16 patients receiving usual care. As this pilot study is underpowered to detect between group differences at the end of the intervention, we will base our primary analysis on the within group difference of the intervention group. Based on an anticipated pre-post difference of 1500 steps/day and a SD of 2000 steps/day, we need 16 individuals for a power of 80% using an  $\alpha$  level of 0.05 (two-sided, paired T test). The control group will be used to address the repeatability of the activity measures. Both groups will be needed for a power calculation of the subsequent randomized trial.

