#### **Activity monitor (Dynaport movemonitor)**

The Dynaport® is the activity monitor that will be used in this study. It will be carried one week prior to visit 3 and one week prior to visit 4. It is an electronic device that is used to measure the patient's physical activity level (number of steps/day). The activity monitor provides valuable information of different aspects (i.e. different output parameters: time spent in at least moderate physical activity (MVPA), walking time, intensity of moving during walking, ...) on physical activity, directly from the wearer, in real time and in real life. This monitor will be worn during the time patients are awake, and must not be worn during bathing or water sports activities. Mean daily step count has been chosen as primary outcome.

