### **5. Selection and withdrawal of subjects**

#### **5.1 Inclusion criteria**

1. Patients diagnosed with stage III or stage IV NSCLC who have a documented disease control (stable disease, partial or complete response defined by RECIST V1.1) at least 6 months after start of first line treatment. Stage III patients can only be included, if first line treatment consisted of concurrent chemoradiotherapy and a consolidation immunotherapy if indicated (if PDL1 > 1% and no potential contraindications for immunotherapy). Stage IV patients, should have received only immunotherapy (PDL1 > 50%) or a treatment of at least 4 cycles of a platinum based chemotherapy. Maintenance therapy with chemotherapy and/or immunotherapy is allowed. Administration of local radiotherapy is allowed. Patients with documented disease control can be included in the study until 2 years after starting up initial treatment.
2. > 18 years
3. Patients who are able to engage in a remote coaching program through the use of a smartphone

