### Visit 2 (screening visit (run-in))

During visit 2 (run-in) all eligible patients who have signed the informed consent will enter the run in epoch of 1 to 2 weeks.

Patients are asked about their medical history (baseline demographic data) and their previous respiratory treatment including their oncological stage and type. Co-morbidities will also be assessed and a basic lung function will be performed.

On visit 2 patient will receive a Dynaport movemonitor to wear one week before visit 3. For patients where the run in period is more than one week, they will receive a telephone reminder to wear PROactive monitors. Patients are instructed to wear the device during waking hours. A measurement of more than 8 hours of wearing time will be defined as a 'valid day). The tri-axial accelerometer will capture steps waked per day, movement intensity and time spent in sitting, lying walking and high-intense activities.

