### **9.2 Analysis**

Within group comparison of the primary and secondary outcome parameters will be analyzed by paired T-test statistics for parametric distributions and Wilcoxon signed-rank test test for non-parametric distributions. Linear and logistic regression will be used to address determinants of treatment response. Ancova analyses will be used to compare between group differences at 8 weeks, adjusted for baseline differences and possible confounders. Data will be presented as mean  $\pm$  SD. Statistical significance will be set at  $p<0.05$  for all the analyses.

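### Can the control group address the repeatability of the activity measures when its two recordings lie 8 weeks apart with activity advice in between?

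*Protocol*

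**What the plan says.** Section 9.1 bases the primary analysis on the within-group change of 16 coached patients and gives the 16 controls this task: "The control group will be used to address the repeatability of the activity measures". The next sentence adds a second use: "Both groups will be needed for a power calculation of the subsequent randomized trial". Section 9.2 does not mention repeatability. For the comparison of the groups it states: "Ancova analyses will be used to compare between group differences at 8 weeks".

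On the timing of the recordings, the activity monitor text under section 3.4 says: "It will be carried one week prior to visit 3 and one week prior to visit 4". Section 6.1 (Visit 2) agrees: "On visit 2 patient will receive a Dynaport movemonitor to wear one week before visit 3". Sections 3.6 and 6.1 place V4 8 weeks after V3. The flowchart in section 3.8 lists these two 7-day recordings and no others.

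On what happens between the recordings, section 3.6 says: "Patients in both groups will receive a brochure during V3 explaining the importance of physical activity with recommendations to improve it", and then: "This brochure will be discussed together with the patients". Section 5.1 says: "Maintenance therapy with chemotherapy and/or immunotherapy is allowed". The same section requires documented disease control at least 6 months after the start of first-line treatment.

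**The concern.** Repeatability, in the strict sense, is the agreement of repeated measurements while the measured quantity stays the same. Here 8 weeks pass between the recordings. In that time the protocol itself gives advice intended to raise activity, and some patients may be on maintenance treatment. If controls change by different amounts, that real change enters the spread of their differences, and two recordings per patient cannot separate it from monitor error. A report that called the result the repeatability of the activity measures would then credit the monitor with more error than it has. No analysis plan could undo this, because no short-interval repeat recording is made.

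A within-week reading, using agreement between the days of one recording, seems not to explain the sentence: all 32 patients have a recording week before V3, so there would be little reason to name the controls. The natural reading is therefore the V3-to-V4 comparison, which is where the difficulty lies.

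**Working it through.** **The plan's own figure.** Inputs from section 9.1: difference 1500 steps/day, SD 2000 (read as the SD of the pre-post difference, since the test is paired), two-sided α 0.05, power 80%. With the noncentral t, noncentrality (1500/2000)·√n and n − 1 degrees of freedom, power is 77.1% at n = 15 and 80.06% at n = 16. The stated 16 is reproduced, and it uses nothing from the control group.

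**What the control differences measure.** Let σe be the error SD of one weekly mean and σc the between-patient SD of true 8-week change. Then

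SD(difference)² = 2σe² + σc²

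The usual repeatability SD is SD(difference)/√2, so

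apparent / actual error SD = √(1 + σc² / (2σe²)).

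The protocol gives neither σe nor σc, so the inputs below are assumptions in steps/day.

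| σe | σc = 0 | σc = 500 | σc = 1000 | σc = 1500 |
|---|---|---|---|---|
| 750 | 1.00 | 1.11 | 1.37 | 1.73 |
| 1000 | 1.00 | 1.06 | 1.22 | 1.46 |

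Example: σe = 1000 and σc = 1000 give √(1 + 1,000,000/2,000,000) = √1.5 = 1.22. A simulation of 200,000 patients gave an apparent error SD of 1224 against 1000.

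**A change common to all patients.** A uniform shift moves the mean difference and leaves its SD alone. With σe = 1000 and σc = 0, the simulated apparent error SD was 997 without a shift and 999 with a shift of 500. The concern is thus confined to change that differs between patients.

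**Sampling error with 16 controls.** The 95% limits for an SD on 15 degrees of freedom are √(15/χ²), or 0.74 to 1.55 times the estimate. An observed SD of 2000 would carry limits of 1477 to 3095. Most of the factors in the table lie within that uncertainty.

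**What the later trial needs.** A power calculation for 8-week change uses SD(difference), which contains both components. Suppose SD(difference) is 2000 and half its variance is true change. The pure-error SD of a difference is then 2000·√0.5 = 1414. Since sample size scales with the variance, planning on 1414 would give (1414/2000)² = 0.50 of the patients required. The mixed figure that the controls supply is the one to use.

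**Would a day-to-day reliability analysis be better?** One could take the standard error of the weekly mean from the days within the V3 week and treat it as a lower bound on between-week error. That bound is not guaranteed. Seven consecutive days cover each weekday once, so a stable weekday pattern cancels between weekly means but inflates the day-to-day variance. Assume a residual day SD of 1500 and a weekday-pattern SD of 1000 (divisor 7):

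- within-week standard error: √[(1500² + 1000²·7/6)/7] = √488,095 = 699
- between-week error SD with no week-to-week component: √(1500²/7) = 567
- between-week error SD with a week-to-week SD of 300: √(321,429 + 90,000) = 641
- between-week error SD with a week-to-week SD of 500: √(321,429 + 250,000) = 756

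The within-week figure exceeds the between-week error in the first two cases and falls below it only in the third.

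**The case for a change.** The best argument for a change is that it costs one sentence and removes a claim the design cannot support. Section 9.1 gives half the sample this role. The interval and the advice are fixed by the protocol itself, so the matter cannot be put down to detail left to an analysis plan. The same number under a plainer name, the SD of 8-week change under usual care plus brochure, would serve the announced power calculation directly.

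The factual part of this stands: the control differences are not a pure measure of monitor error, and the word is loosely used. The rest does not carry a change to the plan, for three reasons.

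- The protocol never says that the V3-to-V4 spread is measurement error. The primary analysis is an uncontrolled 8-week pre-post change, so a natural reference is how well the same measure reproduces over the same 8 weeks without coaching. Only the controls have two recordings without coaching, which is a reason to name them under either reading.
- The definition and statistic of a subsidiary analysis are commonly left to the analysis plan.
- Patient-specific change in controls is plausible but not shown. Maintenance treatment is permitted, not required, and patients are selected for documented disease control.

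**Conclusion.** The concern identifies a loose term, not a fault in the design. The V3-to-V4 spread in controls is measurement error plus any patient-specific change over 8 weeks under usual care with a brochure. If it were read as pure error, the overstatement would be a factor of 1.00 to 1.73 over the assumed ranges (σe 750 or 1000, σc 0 to 1500 steps/day); the protocol cannot narrow this. No test, threshold or sample size depends on the figure. The paired test with n = 16 and the ANCOVA are unaffected, and the later power calculation needs the mixed SD in any case. A new label would leave every number as it is, and the obvious additional analysis, within-week reliability offered as a lower bound, is not sound in general. An analyst who reports the figure as variability over 8 weeks in uncoached patients meets the concern without any change to the protocol.
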